## 1. STUDY SYNOPSIS

Study Title	Multicentric phase II trial to evaluate the efficacy and safety of Ibrutinib in combination with rituximab in patients with indolent clinical forms of Mantle Cell Lymphoma
Protocol Number:	GELTAMO IMCL-2015
Protocol Version:	3.2 September 16th, 2020
Chief Investigator	Dra. [name] Haematology Department Hospital Clinic de Barcelona [name] [name] [contact]
Type of application	Clinical trial of a marketed medicinal product in new indication.
Study phase	Phase II
Indication	Untreated patients with indolent clinical forms of Mantle Cell Lymphoma
Study design	Phase II study with a two-stage design to evaluate efficacy and safety of ibrutinib in combination with rituximab (I+R) in untreated patients with indolent clinical forms of MCL.  An extensive biological study will be conducted in order to further characterize this population of MCL patients and evaluate the response obtained with the mutational profile of the tumor.
Number of subjects	50 patients
Study duration	The maximal trial duration will be <del>seven</del> 10,5 years with <del>3</del> 3,5 years of recruitment. The study can stop earlier based on the results obtained in the first 15 recruited patients.  Version 3.2: September 16th, 2020
Primary Objectives	1. To assess the efficacy of I+R combination as a therapeutic alternative to immuno-chemotherapy (R-CHOP regimen) in indolent clinical forms of MCL
Secondary Objectives	1. To evaluate the efficacy of I+R combination along time in terms of ORR, PFS, response duration, OS, MRD analysis) 2. To determine the safety and tolerability of ibrutinib in combination with rituximab 3. Biological characterization of indolent clinical forms of MCL and their response to I+R by genomic studies

Primary Endpoints	1. Rate of complete remission (CR) achieved at 12 months of I+R combination.

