## **2.2 OBJECTIVES**

### **Primary**

1. To explore the efficacy of I+R combination as a therapeutic alternative to immuno-chemotherapy (R-CHOP regimen) in indolent forms of MCL by assessing the rate of complete responses achieved at 12 months of treatment.

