## 5. STUDY DEVELOPMENT AND RESPONSE ASSESSMENT

### 5.1 STUDY ENDPOINTS

#### Primary Endpoint:

1. Rate of complete remission (CR) achieved at 12 months with Ibrutinib in combination with Rituximab. All the patients will be evaluated with PET-CT and bone marrow biopsy at that point and the international response criteria will be applied (13).

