### 5.3.2 Response assessment:

Percentage of complete remissions at 12 months: is defined as the percentage of patients who are alive and in complete response at 12 months from the date of treatment initiation. All patients will be evaluated with PET- CT and bone marrow biopsy at that time.

Overall response rate: Proportion of patients who experienced PR or CR.

Progression free survival (PFS): defined as the time between start of treatment and the first documentation of recurrence, progression, or death in the event of no documented recurrence, or start of a new anti – lymphoma treatment, due a refractory or persistent disease.

Response duration: is defined as the time from the documentation of tumor response to disease progression or death, in the event of no documented recurrence, or start of a new anti – lymphoma treatment because of refractory or persistent disease.

Overall survival (OS): is defined as the time between the start of treatment and death from any cause. Patients that are withdrawn from the trial or lost of follow-up, will be censored with the date of last contact. Patients who are still alive at the end of the study will be censored at that time.

Minimal residual disease negative rate: is defined as the proportion of subjects who are MRD negative (ie, less than the lower limit of detection for the MRD assay). All patients with a valid MRD result (negative or positive) will be included in this analysis.

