## **6.6. CONTACT DATA FOR SAE, PREGNANCY, DEATH AND QUALITY CLAIMS NOTIFICATIONS, SPECIAL SITUATION REPORTS**

**DEPARTAMENTO DE INVESTIGACIÓN MFAR, S.L.**

**[contact]**

**e-mail: [[contact]](mailto:[contact])**

**Version 3.2: September 16th, 2020**

## **7. STATISTICAL CONSIDERATIONS**

Our study proposal is looking for a therapeutic alternative to conventional immunochemotherapy (R-CHOP) in clinically indolent MCL.

This phase II study will explore the feasibility of Ibrutinib plus Rituximab combination in this subset of patients evaluating its capacity of inducing a high response rate with a favourable toxicity profile. In addition, an extensive biological study of the cases will be conducted in order to explore clinic-biological correlations.

We hypothesize that for a CR rate of 30% usually achieved with R-CHOP, the combination of Ibrutinib plus Rituximab will be able to exceed this proportion in 20%.

We propose a Phase II study with a two-stage design with error probabilities  $\alpha$  and  $\beta$  of 0.10 and 0.2 respectively. The optimal design will have an expected sample size of 50 patients (at least 46 patients evaluable for response).

The first stage will consist of 15 patients. If 5 or less complete responses are observed the trial is terminated, otherwise accrual can continue to a total of 50 patients.

For Primary Analysis we plan the evaluation of CR rate at 6 months from the start of therapy. All the patients will be evaluated with Thoracoabdominopelvic CT and bone marrow aspirate at that point. If 5 or less complete responses are observed among the first 15 patients recruited and evaluated, the trial will be terminated.

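### Section 7 labels the 6-month stage-1 look as the primary analysis and leaves the 12-month primary endpoint out of the statistical section

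*Protocol*

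**What the plan says.** Four places set the time point of the primary endpoint at 12 months:

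- Synopsis, Primary Endpoints: "Rate of complete remission (CR) achieved at 12 months of I+R combination".
- Section 2.2, primary objective: "by assessing the rate of complete responses achieved at 12 months of treatment".
- Section 5.1: "Rate of complete remission (CR) achieved at 12 months with Ibrutinib in combination with Rituximab".
- Section 5.3.2: the CR percentage "is defined as the percentage of patients who are alive and in complete response at 12 months from the date of treatment initiation".

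Sections 5.1 and 5.3.2 also attach the method to the endpoint. In Section 5.1: "All the patients will be evaluated with PET-CT and bone marrow biopsy at that point". The Synopsis endpoint line and the Section 2.2 objective give the time point only.

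Section 7 says: "For Primary Analysis we plan the evaluation of CR rate at 6 months from the start of therapy". It continues: "All the patients will be evaluated with Thoracoabdominopelvic CT and bone marrow aspirate at that point". The next sentence is the stopping rule: the trial ends if 5 or fewer CRs are seen in the first 15 patients. The 30% reference rate and the 20-point gain carry no time point, and no final success threshold is given.

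**The concern.** Section 7 is where an analyst looks for the quantity to be tested against 30%. The only time point there is 6 months, and the only methods there are CT and aspirate. Time point, imaging and marrow assessment all differ from the endpoint in Section 5.1.

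The methods are not interchangeable. Annex VII defines complete response separately for PET-CT and for CT. A PET-CT score of 1 to 3 counts as complete even with a residual mass, whereas the CT column has a nodal size criterion and asks for normal marrow morphology. One patient could be a complete responder in one column and not in the other.

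If Section 7 were followed as written, the trial's hypothesis would be judged on a rate that is not its endpoint. A statistical analysis plan could not settle this alone, because a plan that followed Section 7 would contradict Section 5.1.

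**Working it through.** **1. The texts side by side**

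| | Synopsis, 2.2 | 5.1, 5.3.2 | 7 |
|---|---|---|---|
| Time point | 12 months | 12 months | 6 months |
| Imaging | not in the endpoint line | PET-CT | CT |
| Marrow | not in the endpoint line | biopsy | aspirate |
| Patients | not stated | all | all |

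**2. What the 6-month look was for.** The version 2.0 entry in the revision sheet gives as rationale that stage 2 opens on 6 or more CRs at the sixth-month evaluation instead of at 12 months, and that the study's objectives are unaffected. As an amendment log it does not govern, but it agrees with the stop rule that follows the disputed sentence in Section 7. Both point to a stage-1 gate.

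**3. Whether the 6-month analysis matches the visit plan.** Section 7 has all patients undergo an aspirate at 6 months. Section 5.2.2.2 asks only that it be considered, and only in forms confined to marrow and blood. The two do not agree.

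**4. Reproducing the design.** Inputs from Section 7: p0 = 0.30, p1 = 0.30 + 0.20 = 0.50, alpha 0.10 (sidedness not stated), beta 0.20, 15 patients in stage 1, stop at 5 or fewer CRs, at least 46 evaluable. An exact search for Simon's optimal design gives:

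- one-sided alpha 0.05 (0.10 read as two-sided): stop at 5/15, success at 19 or more of 46; attained alpha 0.0499, power 0.803. Stage 1, the stop rule and N = 46 all match;
- one-sided alpha 0.10: stop at 5/15, success at 13 or more of 32; attained alpha 0.0997, power 0.804. Only stage 1 matches.

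The rule of at least 19/46 is therefore inferred, not stated. With 46 patients, the lowest final cut-off that keeps one-sided alpha within 0.10 is 18 (alpha 0.0795, power 0.827); a cut-off of 17 gives 0.1164.

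**5. Illustration: both stages judged on the 6-month rate.** Assume that the true 12-month CR rate is 50% and that 50% to 80% of those CRs are present at 6 months. The 6-month rate q then runs from 0.5 × 0.50 = 25% to 0.8 × 0.50 = 40%. With c the final cut-off,

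P(success) = sum over x = 6 to 15 of C(15,x) q^x (1−q)^(15−x) × P(Y ≥ c − x), where Y ~ Binomial(31, q).

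| 6-month CR rate q | stops at stage 1 | success, c = 19 | success, c = 18 |
|---|---|---|---|
| 25% | 85% | 0.8% | 1.6% |
| 30% | 72% | 5.0% | 8.0% |
| 35% | 56% | 17.2% | 23.2% |
| 40% | 40% | 38.3% | 45.3% |
| 50% | 15% | 80.3% | 82.7% |

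**6. What relabelling alone recovers.** Keep the gate at 6 months but make the final test on 12-month CR (true rate 50%, c = 19), and assume that every 6-month CR persists to 12 months. Power is then 80% if the 6-month rate is also 50%, 71% at 45%, 57% at 40% and 42% at 35%. At 40% and 35% these compare with 38% and 17% when the final test also uses the 6-month rate.

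**The case against.** The protocol has one primary endpoint, stated four times without exception, and the disputed sentence leads straight into the 15-patient stop rule. A reader might infer from the label that the trial has two primary results and that an analyst could choose between them after seeing both. The documents do not support that. The stop rule and the version 2.0 rationale show a gate under the wrong name, and anyone reporting 6-month CR as primary would contradict all four endpoint statements. This part of the objection stands, and it limits the charge to mislabelling and omission.

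The figures are also open to challenge. The final cut-off is not in the protocol. The 5.5-month median time to CR (range 2 to 12) in Section 2.1 is for ibrutinib alone in heavily pre-treated patients, whereas this trial gives the combination to untreated indolent disease. The share of CRs present at 6 months is assumed. The illustration models timing only, because the documents do not say how CT plus aspirate would shift the rate in either direction. This stands too: the digits are conditional.

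What does not stand is that the intent cures the text. The current Section 7 applies its label to all patients, not the first 15, and the 12-month analysis appears nowhere in it.

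**Conclusion.** Section 7 is wrong as written: it gives the name of primary analysis to the stage-1 gate and omits the analysis of the actual primary endpoint. This rests on the text alone and needs no assumption. The conflict in time point is with four places; the conflict in method is directly with two, Sections 5.1 and 5.3.2.

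The size is illustrative. If the 12-month CR rate is 50% and the 6-month rate is 25% to 40%, judging the trial on the 6-month rate gives a chance of success of about 1% to 38% with a cut-off of 19/46, or about 2% to 45% with 18/46, against about 80% intended. Not all of that gap comes from the label. Part of it comes from holding the gate at 6 months, which would remain after the wording is corrected.

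**What to change.** Rewrite the last paragraph of Section 7 to state that:

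- the primary analysis is the CR rate at 12 months by PET-CT and bone marrow biopsy, as defined in Sections 5.1 and 5.3.2, compared with 30%;
- the final success threshold of the two-stage design is a stated number of CRs out of a stated number of evaluable patients, consistent with the declared alpha and its sidedness;
- the 6-month evaluation of the first 15 patients serves only the decision to open stage 2 and is not the primary analysis.

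Reconcile the 6-month aspirate wording in Section 7 (all patients) with Section 5.2.2.2 (to be considered, in marrow and blood forms only).

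The cost is a short amendment. The 12-month analysis needs no new data, since PET-CT and biopsy are already scheduled for every patient at that visit.

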Among the new drugs under development, Ibrutinib is showing an impressive efficacy in relapsed and refractory patients (8-9), which has led to its approval by the FDA and EMA agencies, in this context. Ibrutinib alone is able to induce 68% of responses in heavily pre-treated patients with MCL, including up to 21% of complete responses. The median time to achieve a CR was of 5.5 months (2-12 months). Moreover, ibrutinib in combination with rituximab appears to be a feasible and highly effective treatment in the relapse and refractory setting. The overall response rate was superior to 85%, including CR in 38% of cases. Moreover, MCL patients with a lower proliferation index (Ki-67 < 50%) achieved CR in up to 48% of the cases.

These promising results provide an excellent opportunity of treating in front-line selected MCL patients with a chemo-free approach, probably this resulting in a more efficient and less toxic manner of treating these patients. In this sense, we hypothesize that MCL cases with an indolent clinical presentation, not requiring the immediate initiation of therapy, would be excellent candidates to receive Ibrutinib in combination with rituximab in first line treatment.

Likewise, this trial offers an unbeatable platform to comprehensively and prospectively study the biological characteristics of this selected group of patients, which will allow to improve their future clinical-biological identification and to deepen the knowledge of the response and resistance mechanisms. to new drugs. For this reason it has been contemplated to associate an extensive and complete molecular study, which includes the total sequencing of exomes from these patients.

MCL similarly to what has been observed in other lymphoproliferative disorders, could show subclonal heterogeneity even at diagnosis and this fact might condition the ulterior clinical behaviour of the tumor (10). In addition, there has been recently described the involvement of the alternative NF- $\kappa$ B pathway in the resistance of BCR inhibitors by the identification of several mutations in NF- $\kappa$ B regulatory genes that confer resistance to these biological agents (11).

This observation enhances the need of collecting fresh samples in the setting of well-designed trials to elucidate the role of new therapies in these patients. As peripheral blood is involved in a

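### The stated 80% power for 12-month CR holds only if the CR rate is already about 50% at the 6-month stage-1 look, and the protocol gives no 6-month rate

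*Protocol*

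**What the plan says.** Section 7 sets one pair of response rates, without a time point: "We hypothesize that for a CR rate of 30% usually achieved with R-CHOP, the combination of Ibrutinib plus Rituximab will be able to exceed" that figure by 20%. I read this as 30% versus 50%. The error probabilities are "of 0.10 and 0.2 respectively", and the sample size reads: "The optimal design will have an expected sample size of 50 patients (at least 46 patients evaluable for response"). The stage-1 rule is "If 5 or less complete responses are observed the trial is terminated, otherwise accrual can continue to a total of 50 patients".

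The last paragraph of section 7 places the primary analysis, and this same rule, on the CR rate at 6 months, with thoracoabdominopelvic CT and a marrow aspirate in all patients: "If 5 or less complete responses are observed among the first 15 patients recruited and evaluated, the trial will be terminated".

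The synopsis, section 5.1 and section 5.3.2 define the primary endpoint as CR at 12 months. Section 5.1 adds: "All the patients will be evaluated with PET-CT and bone marrow biopsy at that point". Section 5.2.2.2 only asks sites to consider the 6-month aspirate, and only in disease confined to marrow and blood. The revision sheet records, for version 2.0, that the look was moved from 12 to 6 months to limit recruitment time.

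The only figure on the timing of CR is in section 2.1: "The median time to achieve a CR was of 5.5 months (2-12 months"). It follows the results for ibrutinib alone in heavily pre-treated patients.

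**The concern.** A stage-1 boundary is calibrated to the response rate at the look where it is applied. Here one boundary and one beta serve a 12-month PET-CT and biopsy endpoint, while the look uses a 6-month CT and aspirate outcome. A patient who reaches CR between months 6 and 12 counts against the regimen at the look and for it at the end. If such patients are common, a regimen that meets its 12-month target can be stopped for futility more often than beta 0.2 implies. No 6-month CR rate, recalculated boundary or recalculated power appears in the current text.

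**Working it through.** **Inputs.** From section 7: p0 = 0.30, p1 = 0.50, alpha 0.10, beta 0.20, n1 = 15, stop at 5 or fewer CR, 46 evaluable. Not in the protocol, so assumed: the 6-month CR rate p6, the final cut-off, and whether alpha is one- or two-sided.

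**Step 1: reproduce the stated design.** An exact search for the optimal two-stage design with one-sided alpha 0.05 (two-sided 0.10) and beta 0.20 gives stage 1 at 5/15 and success at 19 or more of 46. The exact type I error is 0.0499 and the power 0.803. This matches 15, 5 and 46. With one-sided alpha 0.10 the optimal design has the same stage 1 but 32 patients (success at 13 or more), so 46 fits only the two-sided reading.

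**Step 2: separate the look from the final test.** Let p12 be the 12-month CR rate, and assume that every 6-month CR is still a CR at 12 months.

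- P(stop) = P(Bin(15, p6) ≤ 5).
- A patient not in CR at 6 months is in CR at 12 months with probability q = (p12 − p6)/(1 − p6).
- Power = Σ over x = 6 to 15 and y = 0 to 15 − x of b(x; 15, p6) · b(y; 15 − x, q) · P(Bin(31, p12) ≥ 19 − x − y), where b is the binomial probability.

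For example, at p12 = 0.50 and p6 = 0.40, q = 0.10/0.60 = 0.167, P(stop) = 0.403 and power = 0.575.

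**Results for p12 = 0.50:**

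| 6-month CR | P(stop at stage 1) | Power, 19/46 | Power, 13/32 |
|---|---|---|---|
| 50% | 15% | 80% | 80% |
| 48% | 19% | 77% | 77% |
| 45% | 26% | 71% | 71% |
| 40% | 40% | 57% | 58% |
| 35% | 56% | 42% | 42% |
| 30% | 72% | 27% | 27% |

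The last column shows that the reading of alpha hardly matters. The chance of passing the look caps power whatever the final cut-off is: at 40% CR by 6 months the cap is 1 − 0.403 = 0.597.

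**Step 3: relax persistence.** Suppose 40% of patients are in CR at both times, 10% at 6 months only and 10% at 12 months only. Both rates are then 50%, P(stop) is 15% and power is 0.788.

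**Step 4: type I error at p12 = 0.30, cut-off 19/46.** With persistence it is 0.050 at p6 = 0.30, 0.033 at 0.25 and 0.016 at 0.20. Without persistence it need not fall: with 27% in CR at both times, 10% at 6 months only and 3% at 12 months only, it is 0.055, still below the stated 0.10.

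**The case against.** Four points can be made for the plan.

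- **No 6-month rate is known.** The 5.5-month median comes from single-agent ibrutinib in heavily pre-treated disease. This trial adds rituximab and enrols untreated, asymptomatic patients with low tumour burden. A reader might infer from the median that about half of the CRs come after month 6, so that the stated beta is simply false. The documents do not support that: if 6-month CR is 50%, the design still gives about 80%. This point stands, and the loss can only be shown as a range.
- **Early CRs can be lost, and CT-based and PET-based CR are different classifications.** This also stands. The table in step 2 describes one direction of change, and step 3 shows a milder case. For the same reason, a general statement that type I error falls would be too strong.
- **Section 7 attaches no time point to 30% and 50%.** Read literally, the whole test could be at 6 months, and 80% would then be consistent for that outcome. But section 7 would then contradict the 12-month primary endpoint, so the text needs correction on either reading.
- **The earlier look was a disclosed choice to protect recruitment time.** Futility looks on an earlier outcome are accepted practice. That justifies the look, but not an unqualified beta for the 12-month endpoint.

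**Conclusion.** The point holds in conditional form. The stated beta of 0.2 describes the 12-month endpoint only if CR at the 6-month look is also about 50%, an assumption the protocol neither states nor supports. There is little slack: under persistence and a 19/46 cut-off, power is 80.3% at a 6-month CR of 50%, 77% at 48% and 57% at 40%. These figures rest on a 12-month CR of 50%, persistence of early CRs and a final cut-off that the protocol does not give.

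The main cost is a false stop for futility, which rises from 15% to 40% at a 6-month CR of 40%. A reader might infer that a positive final result would be unreliable. The calculation does not show that: type I error falls if CRs persist, and stayed near 0.05 in the example where some are lost.

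**What to change.** 1. Reconcile sections 5.1, 5.2.2.2 and 7 on the time point and assessments of the primary analysis, including whether the 6-month aspirate applies to all patients.
2. If 12-month CR remains primary, describe the 6-month look as a futility look on an earlier outcome, not as the primary analysis.
3. Replace the unqualified beta of 0.2 with power and early-stopping probability over a stated range of 6-month CR rates, and say whether early CRs are assumed to persist.
4. State the final cut-off for 12-month CR and whether alpha 0.10 is one- or two-sided.

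The cost is wording and a short exact calculation; the downside is that the stated power becomes less favourable. Moving the look back to 12 months, or lowering the cut (for example to stopping at 2 or fewer of 15), is not part of this fix. Each is a trade-off: with a 6-month CR of 60% of the 12-month rate, the lower cut would stop a regimen with 30% CR only 48% of the time. It is also probably too late, since the synopsis puts the end of recruitment at December 2019 and the current version is dated September 2020.

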## **8. MOLECULAR SUB-STUDY**

Peripheral blood samples will be collected prior the start of therapy in order to obtain DNA and RNA purified of tumor samples and DNA and RNA of paired non tumor samples. IGHV mutational assessment and genomic studies including whole exome sequencing (WES) and the analysis of DNA copy number alterations will be conducted in those pretreatment samples.

Lymph node or other tissue biopsies (either frozen or FFPE tissue) diagnostic of MCL will be collected when available to perform histological review, create a TMA and to obtain tumor DNA and RNA in order to expand the genomic studies especially in those cases without peripheral blood involvement.

A new tumor sample collection either in peripheral blood and/or tissue will be obtained whenever possible in those patients presenting progressive or relapsed disease to I+R in order to allow conducting second time-point WES studies. These studies will focus particularly in the study of the mechanisms of ibrutinib resistance.

